6. ANALYSIS POPULATION

Per-Protocol (PP) Population

Patients will be eligible for inclusion in the PP population if they:

- Met the inclusion/exclusion criteria as defined in the protocol at Visit 1 and 2
- Did not take any prohibited medications throughout the study
- Did not have any significant deviations from the protocol
- Did not develop any concurrent vaginal infection or illness exhibiting symptoms similar to atrophic vaginitis, or symptoms that in the Investigator's opinion would interfere with primary and secondary endpoint assessments
- Completed the last study visit (Visit 3) Day 8 ± 1 .
- Were compliant with dosing between 75%-125% of the required doses (6 8 doses), and did not miss more than 1 dose
- Any patient who withdrew from the study because of lack of efficacy will be included
 in the PP population as a Non-Responder. Patients who discontinue early for other
 reasons should be excluded from the PP population and included in the mITT
 population using Last Observation Carried Forward (LOCF).

Modified Intent-to-Treat (mITT) Population

The mITT population will include all patients in the PP population, AND patients who:

- Administered at least one dose of randomized study medication and
- Had a post-randomization evaluation

Safety Population

The safety population will include all patients who are randomized and administered at least one dose of study drug.

7. STUDY ENDPOINTS

Primary Efficacy Endpoint

Estradiol Vaginal Cream USP, 0.01%

Protocol/Study Number 71436001

The primary efficacy endpoint is the proportion of patients in the PP population that are identified as "Responders" at the end of the treatment period evaluated on Day 8 ± 1 .

A responder is defined as a patient with at least a 25% reduction from baseline in the sum of % basal/parabasal + % intermediate cells on vaginal cytology AND vaginal pH < 5.0 with a change from baseline vaginal pH of at least 0.5.

Secondary Efficacy Endpoint

The secondary efficacy endpoint is the proportion of patients in the PP population that are identified as "Treatment Success" at the end of the treatment period evaluated on Day 8 ± 1 .

A "Treatment Success" is defined as a score of 0 or 1 at Day 8 ± 1 for the symptom identified at baseline as the most bothersome. This evaluation is to be based on patient self-assessed symptoms of vulvar and vaginal atrophy on a scale of 0 to 3 where 0 = none and 3 = severe.

8. STATISTICAL ANALYSIS METHODS

If not otherwise specified, statistical significance is defined as p<0.05 and is two-tailed. Data will be summarized with respect to demographic and baseline characteristics, efficacy variables and safety variables.

For categorical variables, the number and percent of each category within a parameter will be calculated for non-missing data. For continuous variables, statistics will include n, mean, standard deviation, median, minimum and maximum values.

All statistical analyses will be conducted using SAS®, Version 9.4 or higher. Datasets will be prepared using headings from Clinical Data Interchange Consortium (CDISC) Study Data Tabulation Model (SDTM) implementation for human clinical trials and ADaM (Analysis Dataset Model).

8.1 Baseline Characteristics

8.1.1 Patient Disposition

The patient accountability and disposition information will be summarized by study treatment group. The number of patients enrolled, randomized, and the number of patients in each analysis population will be tabulated. In addition, completion status and primary reason for withdrawal will be summarized by study treatment group.

Estradiol Vaginal Cream USP, 0.01%

Protocol/Study Number 71436001

8.1.2 Demographic and Other Baseline Characteristics

Baseline comparability of all treatment groups will be evaluated separately in the PP, mITT and Safety populations. The following baseline demographics (determined from their initial study visit) will be evaluated:

- Age (years)
- Gender (male/female)
- Ethnicity (Hispanic/non Hispanic)
- Race (White, Black/African American, Native Hawaiian or Other Pacific Islander, Asian, American Indian or Alaska Native, Other)
- natural or surgical menopause
- duration of postmenopausal status
- baseline signs and symptoms
- baseline % of the three major vaginal wall cell types (basal/parabasal cells, intermediate cells and superficial cells)
- vaginal pH

Summary tables by treatment group will be presented. Continuous variables will be summarized using descriptive statistics (n, mean, standard deviation, median, minimum, maximum).

Categorical variables will be summarized using frequencies and percentage. Baseline treatment comparisons will be presented using Cochran-Mantel-Haenszel test for the categorical variables, and Analysis of Variance for the continuous variables.

All data will be listed by treatment and patient.

8.1.3 Medical History

At Visit 1 patients will be questioned about medical history, including acute and chronic medical history and medical history relevant to their vaginal atrophy. At Visit 2 medical history will be reviewed and updated if changes have occurred.

Medical history data will be listed by treatment and patient.

8.1.4 Concomitant Medications

At Visit 1 patients will be questioned about all concomitant medication use within the previous 6 months.

Estradiol Vaginal Cream USP, 0.01%

Protocol/Study Number 71436001

All prior and concomitant medications taken since screening until the end of the study will be listed by treatment and patient.

8.1.5 Physical Exam

At Visit 1 the Investigator will perform a general physical exam including pelvic exam and breast exam. At Visit 3 the Investigator will perform a general physical exam including pelvic exam, any negative findings on exam should be reported as Adverse Events.

Physical examination results will be listed by treatment and patient.

8.1.6 Laboratory Evaluations

All patients will have a blood sample taken for evaluation of serum FSH levels. Serum FSH will be evaluated by a central clinical laboratory. Patients must have a Serum FSH > 40mIU/ml to be eligible for participation in the study.

All patients will have a blood sample taken for fasting triglyceride testing. These samples will be sent to the central laboratory for testing. Patients with fasting triglyceride values > 350 mg/dL will not be eligible for inclusion in the study.

Laboratory evaluation results will be listed by treatment and patient.

8.1.7 Dosing Compliance

Dosing compliance will be checked by site staff at Visit 3 by reviewing patient diary entries. Patients will be considered compliant with dosing if they administer 75% - 125% of the required number of doses, and do not miss more than 1 dose.

Drug administration and dosing compliance will be listed by treatment and patient.

8.2 Efficacy Analyses

The following symptoms (see Appendix A for detailed rating scales) will be evaluated at Visits 1, 2 and 3 by the blinded clinical staff or Investigator.

Symptoms	Rating Scales
Vaginal Dryness	0=None, 1=mild, 2=moderate, 3=severe
Vaginal/Vulvar irritation/itching	0=None, 1=mild, 2=moderate, 3=severe
Dysuria	0=None, 1=mild, 2=moderate, 3=severe
Vaginal Pain associated with Sexual Activity	0=None, 1=mild, 2=moderate, 3=severe
Vaginal Bleeding	0= Absent, 1= Present

The patients will be asked to identify which symptom is considered to be the most bothersome symptom at Visit 1 and Visit 2. Vaginal Pain associated with Sexual Activity or Vaginal

Estradiol Vaginal Cream USP, 0.01%

Protocol/Study Number 71436001

Bleeding are acceptable to be considered most bothersome symptom only if patient is currently sexually active and plans to remain so throughout the study.

8.2.1 Analysis of Primary Efficacy Endpoint

Therapeutic Bioequivalence Analysis

Therapeutic equivalence of the Test product to the Reference product based on the primary endpoint will be evaluated in the PP population after the end of treatment on Day 8 ± 1 .

Based on the usual method used in OGD for binary outcomes, the 90% confidence interval for the difference in success proportions between test and reference treatment should be contained within [-0.20, +0.20] in order to establish equivalence.

The compound hypothesis to be tested is:

$$H_0: P_T - P_R < -.20 \text{ or } P_T - P_R > .20 \text{ versus}$$

$$H_A: -.20 \le P_T - P_R \le .20$$

where P_T = cure rate of test treatment

 $\vec{P_R}$ = cure rate of reference treatment.

Let

 n_T = sample size of test treatment group

 cn_T = number of cured patients in test treatment group

 n_R = sample size of reference treatment group

 cn_R = number of cured patients in reference treatment group

$$\widehat{P}_T = c n_T / n_T$$
 $\widehat{P}_R = c n_R / n_R$, and

$$se = (\hat{P}_T (1 - \hat{P}_T)/n_T + \hat{P}_R (1 - \hat{P}_R)/n_R)^{1/2}$$

The 90% confidence interval for the difference in proportions between test and reference will be calculated as follows, using Yates' correction:

$$L = (\hat{P}_T - \hat{P}_R) - 1.645 se - (1/n_T + 1/n_R)/2$$

$$U = (\hat{P}_T - \hat{P}_R) + 1.645 se + (1/n_T + 1/n_R)/2$$

If the 90% confidence interval (calculated using Yates' continuity correction) for the absolute

Estradiol Vaginal Cream USP, 0.01%

Protocol/Study Number 71436001

difference between the proportion of patients considered as "Responders" (at least a 25% reduction from baseline in the sum of % basal/parabasal + % intermediate cells on vaginal cytology AND vaginal pH < 5.0 with a change from baseline vaginal pH of at least 0.5) in the Test and Reference groups is contained within the range [-20%, +20%] then bioequivalence of the Test product to the Reference product will be considered to have been demonstrated for the primary endpoint.

Superiority to Placebo Analysis

The mITT population and LOCF will be used to evaluate the superiority of both the Test and Reference product to Placebo.

For the determination of superiority the proportion of patients who are considered as "Responders" in the test and reference product groups will each be compared to the proportion of "Responders" in the placebo product group. On condition that both the test and the reference group demonstrate statistically greater proportion of "Responders" (p< 0.05, 2-sided) than the placebo group then superiority shall be concluded and the sensitivity of the methodology confirmed.

Summary table with frequency and percentage on the proportion of responders by treatment group will be presented. Treatment comparison for Test vs. Placebo and Reference vs. Placebo will be performed by continuity-corrected Z-tests. The superiority of Test and Reference treatments over the Placebo will be evaluated identically in separate Z-Test analyses.

8.2.2 Analysis of Secondary Efficacy Endpoint

Therapeutic Bioequivalence Analysis

Similar to the analysis for primary endpoint above, therapeutic equivalence of the Test product to the Reference product based on the secondary endpoint will be evaluated in the PP population after the end of treatment on Day 8 ± 1 .

Secondary analysis will compare the proportion of patients considered to be a "Treatment Success" for their most bothersome symptom. A "Treatment Success" is defined as a score of 0 or 1 at Day 8 for the symptom identified at baseline as the most bothersome). If the 90% confidence interval (calculated using Yates' continuity correction) for the absolute difference between the proportion of patients considered as "Treatment Success" in the Test and Reference groups is contained within the range [-20%, +20%] then bioequivalence of the Test product to the Reference product will be considered to have been demonstrated for the secondary endpoint.

To declare therapeutic equivalence of the Test product to the Reference product, bioequivalence

Estradiol Vaginal Cream USP, 0.01%

Protocol/Study Number 71436001

must be demonstrated for only the primary endpoint. Bioequivalence testing of the secondary endpoint will be conducted for supportive information.

Superiority to Placebo Analysis

The mITT population and LOCF will be used to evaluate the superiority of both the Test and Reference product to Placebo.

Similar to the analysis for primary endpoint above, superiority of the Test and Reference products against the Placebo for secondary endpoints will be tested at the 5% significance level (p < 0.05; using two-sided, continuity-corrected Z-test) in the mITT population using last observation carried forward. The superiority of Test and Reference treatments over the Placebo will be evaluated identically in separate Z-Test analyses.

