9.3 Selection of Study Population

9.3.1 Inclusion Criteria

1. Signed Informed Consent that meets all criteria of current FDA regulations.
2. Females aged 30-75 years inclusive who are postmenopausal, defined as follows:
 - a. At least 12 months of spontaneous amenorrhea or 6 months of spontaneous amenorrhea with serum FSH level of > 40mIU/ml.
 - b. At least 6 weeks post-surgical bilateral oophorectomy, with or without hysterectomy.
 - c. Hysterectomy without oophorectomy if of age that investigator believes would have naturally reached 12 months of spontaneous amenorrhea if uterus had remained intact.
3. Have ≤ 5% superficial cells on vaginal smear cytology.
4. Vaginal pH > 5.0.
5. At least one of the following patient self-assessed moderate to severe symptoms of vulvar and vaginal atrophy (VVA) from the following list that is identified by the patient as being most bothersome to her:
 - a. Vaginal Dryness
 - b. Vaginal and/or Vulvar Irritation/Itching
 - c. Dysuria
 - d. Vaginal Pain associated with sexual activity
 - e. Vaginal Bleeding associated with sexual activity*
6. “Normal” Screening mammogram completed within 9 months before screening in all patients > 40 years old.
7. Normal clinical breast examination at the Screening Visit.

*provided that patient is currently sexually active and plant to remain so throughout study.

CONFIDENTIAL PROTOCOL

A Randomized, Double-Blind, Placebo-Controlled, Parallel Design, Multiple-Site Study to Evaluate the Therapeutic Equivalence of Estradiol Vaginal Cream USP, 0.01% (Teva Pharmaceuticals, USA) to Estrace® Estradiol Vaginal Cream, USP, 0.01% (Warner Chilcott) in the Treatment of Atrophic Vaginitis

8. Documented papanicolaou (PAP) smear conducted within the previous 12 months with no findings that the Investigator believes would contraindicate the use of topical vaginal estradiol.
9. Patients with an intact uterus should have vaginal ultrasonography results to confirm an inactive endometrial lining, defined as endometrial thickness less than 4 mm.

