10.5 Efficacy Endpoints

Primary Efficacy Endpoint

The primary efficacy endpoint is the proportion of patients in the PP population that are identified as “Responders” at the end of the treatment period evaluated on Day 8 + 1.

A responder is defined as a patient with at least a 25% reduction from baseline in the sum of % basal/parabasal + % intermediate cells on vaginal cytology AND vaginal pH < 5.0 with a change from baseline vaginal pH of at least 0.5.

Secondary Efficacy Endpoint

The secondary efficacy endpoint is the proportion of patients in the PP population that are identified as “Treatment Success” at the end of the treatment period evaluated on Day 8 + 1.

A “Treatment Success” is defined as a score of 0 or 1 at Day 8 + 1 for the symptom identified at baseline as the most bothersome. This evaluation is to be based on patient self-assessed symptoms of vulvar and vaginal atrophy on a scale of 0 to 3 where 0 = none and 3 = severe. Refer to Appendix B for rating scales.

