10.7 Superiority to Placebo Analysis

Superiority of the Test and Reference products against the Placebo for primary and secondary endpoints will be tested at the 5% significance level ($p < 0.05$; using two-sided, continuity-corrected Z-test) in the mITT population using last observation carried forward. The superiority of Test and Reference treatments over the Placebo will be evaluated identically in separate Z-Test analyses.

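### The secondary Treatment Success superiority tests are valid but leave out the baseline score of the most bothersome symptom, which costs a modest amount of precision

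*SAP*

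**What the plan says.** The secondary endpoint uses a fixed cut. In SAP 8.2.2, Treatment Success "is defined as a score of 0 or 1 at Day 8 for the symptom identified at baseline as the most bothersome". Protocol 10.5 bases it on "self-assessed symptoms of vulvar and vaginal atrophy on a scale of 0 to 3 where 0 = none and 3 = severe".

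Entry is limited to the upper half of that scale. Protocol 9.3.1 item 5 asks for "At least one of the following patient self-assessed moderate to severe symptoms of vulvar and vaginal atrophy (VVA) from the following list", and the qualifying symptom is the one the patient finds most bothersome. Vaginal bleeding is on that list but is scored only "0= Absent, 1= Present" (SAP 8.2).

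The analysis compares crude proportions. In SAP 8.2.2, "superiority of the Test and Reference products against the Placebo for secondary endpoints will be tested at the 5% significance level", in the mITT population with LOCF. Protocol 10.7 adds: "The superiority of Test and Reference treatments over the Placebo will be evaluated identically in separate Z-Test analyses". Test versus Reference uses an unstratified Yates-corrected 90% interval in the PP population, described as supportive.

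Baseline symptoms otherwise appear only in the comparability tables (SAP 8.1.2, T16.1.9.4). The only stratified efficacy analysis is the treatment-by-site check on the primary endpoint (SAP 8.4). Listing L16.2.6.2 has a column for the baseline score of the most bothersome symptom, so the value is captured.

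**The concern.** Under a fixed cut, the baseline score sets how far each patient has to move: one point from 2, two points from 3. It is the baseline value of the outcome itself and a natural prognostic factor for it. An analysis that ignores such a factor leaves explainable variation in the standard error.

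At stake is the precision of the two active-placebo symptom comparisons, each of which has only about 125 placebo patients. The equivalence decision is not at stake, because it rests on the primary endpoint alone.

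**Working it through.** **1. The plan's own figures.** 224 / 0.90 = 248.9, against 250 stated per active arm in the mITT population. 625 / 0.95 = 657.9, against up to 660 randomised. 660 / 5 = 132 on placebo, as in Protocol 7.4. The chain reproduces to rounding. The rates and power behind 224 are blacked out, so that step cannot be checked.

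**2. Inputs.** From the documents: 250 versus 125 patients, two-sided 5%, continuity correction, scores of 2 or 3 at entry. Assumed, because the documents give nothing: placebo success 40%; true effect 15 points within each severity level; share severe w = 0.5; gap g between success in moderate and severe entrants from 0 to 40 points. At g = 30, for example, placebo success is 55% in moderate and 25% in severe entrants, and active success is 70% and 40%.

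**3. Variance attributable to baseline score, at g = 0.30.**
- Crude variance of the difference: 0.55 x 0.45 / 250 + 0.40 x 0.60 / 125 = 0.00099 + 0.00192 = 0.00291.
- Part due to severity: w(1-w)g² x (1/250 + 1/125) = 0.25 x 0.09 x 0.012 = 0.00027.
- Share: 0.00027 / 0.00291 = 9.3%. The same formula gives 1.0%, 4.1% and 16.5% at gaps of 10, 20 and 40 points.

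**4. Chance imbalance is this same component.** The SD of the active-placebo difference in severe share is sqrt(0.25 x 0.012) = 0.0548. Multiplied by the gap, 0.0548 x 0.30 = 0.0164, and 0.0164² = 0.00027, the quantity in step 3. Its 95% range is 1.96 x 1.64 = 3.2 points on the success difference.

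**5. Power and type I error by simulation.** 200,000 trials per setting, planned continuity-corrected Z-test against a continuity-corrected Cochran-Mantel-Haenszel test stratified by baseline score:

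| Gap (points) | Planned Z-test | Stratified test |
|---|---|---|
| 0 | 75% | 75% |
| 10 | 75% | 76% |
| 20 | 75% | 77% |
| 30 | 75% | 79% |
| 40 | 75% | 82% |

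With no true effect, the planned test rejects in about 3.8-4.0% of trials.

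An imbalance in severe share above 10 points in either direction occurs in about 7% of trials at w = 0.5. When it runs against the active arm (gap 30), power of the planned test is 49% and of the stratified test 77%. These cases are already counted in the averages above.

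**6. Dependence on effect size.** Closed form: power = Phi((d - 0.006) / (se x sqrt(1 - R²)) - 1.96), where 0.006 = (1/250 + 1/125)/2, R² is the share from step 3, and placebo success is 40%. At a 30-point gap R² is 0.093, 0.094 and 0.095 for the three effects below:
- d = 0.15, se = 0.0539: 76.1% to 80.0%
- d = 0.20, se = 0.0537: 95.1% to 96.7%
- d = 0.25, se = 0.0532: 99.6% to 99.8%

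This approximation runs about a point above the simulation. At a 40-point gap and d = 0.15 it gives 83.2%.

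**7. Secondary equivalence.** At 224 per arm, 50% success and no true difference, se = sqrt(2 x 0.25 / 224) = 0.0472. Power = 2 Phi((0.20 - 1/224)/0.0472 - 1.645) - 1 = 98.7%, rising to 99.6% at success rates of 30% or 70%. There is almost nothing to gain.

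**The case against.** The case against is strong and most of it stands.

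- **No error is present.** Treatment is randomised, the crude test holds its level, and the protocol and SAP specify the same test. A reader might infer that severity imbalance biases the comparison. It does not: the crude standard error already includes it (step 4), and counting lost precision and chance imbalance as two problems counts one twice.
- **No stated decision depends on it.** Equivalence is declared on the primary endpoint only, and SAP 8.2.1 concludes superiority and study sensitivity from Responders. Secondary superiority is still a planned 5% test, but the plan attaches no further rule to it.
- **The size rests on assumed inputs.** A reader might expect gains of 5 to 10 power points. With half severe, that needs a correlation between severity and success of about 0.4 to 0.5, meaning gaps of roughly 40 to 50 points. The documents give no basis for gaps that large.
- **Baseline symptoms are already compared.** This holds only in part. T16.1.9.4 shows the severity of each symptom and, separately, which one is most bothersome. It does not show the severity of the most bothersome one, which is the relevant quantity.
- **Allocation may be stratified.** Part of the randomisation text is blacked out, so this cannot be excluded. The analysis as written would still ignore any such strata.
- **An SAP-only change would conflict with the protocol.** Correct: Protocol 10.7 and the synopsis fix the Z-test for both endpoints.

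What remains is a small, nearly free gain from a value already collected, available only if it is specified in advance.

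**Conclusion.** The point holds as an optional improvement in precision. Under the stated assumptions (40% placebo success, 15-point effect, 250 versus 125, half severe), stratification adds about 0 to 4 power points for moderate-severe gaps of 0 to 30 points and about 7 to 8 at 40 points. It adds nothing if baseline score does not predict success, and under 2 points at a 30-point gap once the effect reaches 20 points. The direction follows from the endpoint rule and the entry criterion. The size cannot be fixed from the documents.

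The documents do not support reading this as a flaw in validity, in the primary analysis or in the equivalence conclusion.

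**What to change.** Before unblinding, add to SAP 8.2.2, for each active-placebo comparison, a continuity-corrected Cochran-Mantel-Haenszel test (two-sided 5%) with a Mantel-Haenszel risk difference, stratified by baseline score of the most bothersome symptom (2 versus 3). Report the crude continuity-corrected Z-test beside it.

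- **Status.** If the stratified test replaces the Z-test, align Protocol 10.7 and the synopsis. Otherwise label it a prespecified supportive analysis and leave the protocol as it is.
- **Baseline visit.** Symptoms are rated, and the most bothersome one named, at both Visits 1 and 2 (Protocol 9.6.6, SAP 8.2). Name one visit that supplies both the symptom and its score.
- **Bleeding.** Both possible scores, 0 and 1, meet the success cut, so a patient naming bleeding succeeds whatever her outcome. Put these patients in their own stratum, state that it carries no treatment information, and report their number by arm.
- **Secondary equivalence.** Leave the Yates 90% interval unchanged.

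The cost is a few lines of SAP text and one extra row per comparison in T16.1.9.8, with no new data, visits or patients. The downside is that the secondary superiority method no longer matches the primary one, and a small protocol alignment is needed if the stratified test becomes the main one.
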